Participants are randomly assigned to either PAllow or PAvoid with a 1:1 allocation ratio.. To counter potential imbalance in the randomization both stratification and blocking are employed. Stratification by including department (department of sports medicine/ department of occupational medicine) is necessary because of possible differences in clinical practices furthermore stratification by sex and age (± 35 years) are employed. The allocation sequence is computer-generated with permuted random blocks, set up by a data manager outside the project.

Sample size

The sample size is calculated to test the superiority of PAllow over PAvoid based on the change in the SPADI (primary outcome) from baseline to week 26 (primary endpoint). We aim at having a power of 80% to verify an effect equal to or higher than the Minimal Clinical Important Difference (MCID) of 10 points on SPADI at a 5% significance level. A total of 35 patients are required per group to establish this mean difference of 10 points with a common standard deviation of 15 (0–100 scale). To account for dropouts (max 20%), we are planning to include a total of 42 per group (2).

Intervention and datacollection

For both groups the intervention period lasts 26 weeks. During that period, participants in both groups are offered 8 individual on-site sessions with an assigned sports physiotherapist. Additionally, participants have a home exercise program. Two exercise programs were developed with the principal difference being allowing or avoiding pain during the exercises. Data are collected on three occasions at the hospital; at baseline before randomization and to times after; at 26 weeks (post intervention/primary endpoint), and at 1-year (follow-up/secondary endpoint).

4. Statistical analysis plan

Study Population definitions

Intention-to-treat (ITT)

The primary efficacy analysis performed is assessment of the between-group difference in change in the SPADI score after 26 weeks in the ITT population. ITT population is defined as all randomized participants irrespective of compliance or withdrawals. A patient will be considered randomized as soon as intervention/training group is assigned by according to the allocation sequence.

As-observed population (AO)

The AO population is defined as participants who have the outcome of interest assessed at a given time point of interest (i.e. no imputation of missing data), primarily used for demographics presentation.

Per-protocol population (PP)

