An alpha level of 0.05 (two-sided) will be considered statistically significant. All data analysis will be carried out according to the pre-established analysis plan by a statistician who is blinded to the allocated interventions for the analysis. Data analysis is performed in SAS version 9.4 and R version 4.3.1.

5. Timing and implementation of analysis

The analysis of both primary and secondary outcome will be performed at the same time.

The implementation procedure of the SAP for the PASE trial:

- An otherwised not involved research secretary will export the blinded data from the REDCAP Research Database
- The treatment arms will be coded into “A” and “B” thus leaving all others blinded to treatment allocation during analysis

STATISTICAL ANALYSIS PLAN PASE TRIAL

[figure not shown]
- Blinded data will be delivered to VS according to the statistical model requirements
- All analyses will be conducted blinded from allocation to any of the two treatment arms by an external statistician (VS). Before unblinding a consensus document will be described and signed by all authors of the study.

6. Figure legends

[figure not shown]
Figure 1: Flow of participants throughout the study

Figure 2: SPADI at baseline, week 26 and week 52. The graphs illustrate the results from the Intention-To-Treat population with datapoints representing means and error bars indicate 95% CI's. PAllow, allowing pain group; PAvoid, avoiding pain group; SPADI, Shoulder Pain and Disability Index

STATISTICAL ANALYSIS PLAN PASE TRIAL

STATISTICAL ANALYSIS PLAN PASE TRIAL

(This particular figure is made as an example and based on fantasy data)

STATISTICAL ANALYSIS PLAN PASE TRIAL

Table 1 Demographics and Baseline Data for PAallow and PAvoid group^a

Characteristics	PAallow Group (n=xx)	PAvoid Group (n=xx)
Age in years		
Male		
Height in cm		
Weight in kg		
BMI in kg/m ²		
Dominant side affected		
Symptom duration in months		
Smoking		
- Never		
- Not anymore		
- Yes		
Pain medication past 4 weeks		
- 1-4 times a day		
- 2-6 times a week		
- 1-4 times a month		
Less than once a month or never		
Work		
Shoulder demanding job (y/n)		
Working status		
- working full-time/part-time		
- Partially on sick leave		
- Not working		
Sport participation		
- Elite		
- Recreational		
- No		
Primary outcome measure		
SPADI (0-100; 100 = most disabled)		
Secondary self-reported outcomes		
Quick DASH (0-100; 100 = most disabled)		
Quick DASH Work ^c		
Quick DASH Sport ^d		

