Pain in NPRS (0-10); 10 = most pain		
- Pain at rest ^b		
- Pain during daily activity ^b		
- Worst pain past 24 hours ^b		
- Pain at night ^b		
- Pain acceptance during training ^b		
Work Ability Index		

^a Data are reported as mean \pm SD or n (%) unless otherwise indicated.

PAallow, allowing pain; PAvoid, avoiding pain; BMI, Body Mass Index; SPADI, Shoulder Pain and Disability Index; Quick DASH, Disability Arm Shoulder Hand short form; SD, Standard Deviation

^b All pain is measured using Numeric Pain Rating Scale (NPRS)

^c Optional module (answered if working)

^d Optional module (answered if sport participation)

STATISTICAL ANALYSIS PLAN PASE TRIAL

Table 2 Changes From Baseline to 26 and 52 weeks follow-up for primary and secondary outcome (Intention-to-Treat population)								
	From baseline to 26 weeks				From baseline to 52 weeks			
	Within group change ^{a)}		Adjusted ^{a)}		Within group change ^{a)}		Adjusted ^{a)}	
	PAllow (n=x) Change (SE)	PAvoid (n=x) Change (SE)	Between-Group difference on change (95% CI)	p-value	PAllow (n=x) Change (SE)	PAvoid (n=x) Change (SE)	Between-Group difference on change (95% CI)	p-value
Primary Outcome SPADI								
Secondary Outcomes Quick DASH Quick DASH Work ^c Quick DASH Sport ^d								
Pain in NPRS - Pain at rest - Pain during daily activity - Worst pain past 24 hours - Pain at night - Pain acceptance during training								
Work Ability Index								
GRS								
ROM (°) Scaption passive Scaption active External rotation passive External rotation active								
Strength (MVC) (Nm) Scaption External rotation								
Pressure Pain Threshold (kPa)								

STATISTICAL ANALYSIS PLAN PASE TRIAL

^a Adjusted for age, sex and clinic.

PAllow, allowing pain; PAvoid, avoiding pain; SPADI, Shoulder Pain and Disability Index; Quick DASH, Disability Arm Shoulder Hand short form; SE, Standard Error; 95%CI, 95% Confidence Intervals; NPRS, Numeric Pain Rating Scale; GRS, Global Rating Scale; $^\circ$, degrees; MVC, Maximum isometric voluntary contraction; kPa, kilo Pascal

^c Optional module (answered if working)

^d Optional module (answered if sport participation)

STATISTICAL ANALYSIS PLAN PASE TRIAL

Corresponding table is made for the Per Protocol population for supplementary file

Table 3 Changes From Baseline to 26 and 52 weeks follow-up for primary and secondary outcome (Intention-to-Treat population)								
	From baseline to 26 weeks				From baseline to 52 weeks			

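### Does analysing all outcomes together, including pain acceptance during training, undermine the A/B-masked analysis?

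*SAP*

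**What the plan says.** Section 5 (Timing and implementation of analysis) sets out the masking procedure. A research secretary not otherwise involved exports the data, and the arms are coded A and B, "thus leaving all others blinded to treatment allocation during analysis". The data go to an external statistician "according to the statistical model requirements", and that statistician runs every analysis without knowing the allocation. On order, the section says "The analysis of both primary and secondary outcome will be performed at the same time" and "Before unblinding a consensus document will be described and signed by all authors of the study".

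The programs are described in section 3 (Intervention and datacollection): "Two exercise programs were developed with the principal difference being allowing or avoiding pain during the exercises". Tables 1 and 2 list "Pain acceptance during training" among the pain items. Table 1 gives it as a baseline characteristic, and Table 2 as a secondary outcome with between-group differences in change at 26 and 52 weeks. A footnote to Table 1 says that pain is scored on the NPRS. The SAP does not define the item further and gives no expected difference between arms.

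**The concern.** Coding the arms hides the labels, but it cannot hide a result that points to a label. The programs differ in whether pain during exercise is allowed or avoided, and this outcome asks about accepting pain during training. Someone who sees that arm A moved up and arm B did not might guess that A is PAllow. Because all outcomes are analysed together, that guess would be available before the consensus document is signed.

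At stake would be the blinded interpretation in that document and any analytic choice still open, such as the GEE working correlation, which the SAP does not name. Releasing this row only after sign-off looks like a cheap remedy.

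**Working it through.** **The SAP's own figure.** Section 3 (Sample size) uses a difference of 10 SPADI points, SD 15, two-sided 5% and 80% power. The normal formula gives 2 × (15 × (1.960 + 0.842) / 10)² = 35.3, which rounds up to 36. The stated 35 per group is within rounding (power 79.6%). The masking question does not depend on this figure; it only supplies n.

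**What the row could reveal.** Let d be the true difference in mean change divided by the SD of change, and n the number per arm. The observed order of the A and B means matches the true order with probability P0 = Φ(d × √(n/2)). Let q be the probability that the reader's expected direction is right. The arm is then identified with probability P = q × P0 + (1 − q) × (1 − P0). The SAP gives neither d nor q for this item, so every value below is an assumption. With n = 35, √(n/2) = 4.183.

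| d | P0 (q = 1) | q = 0.9 | q = 0.75 | q = 0.5 |
|---|---|---|---|---|
| 0 | 0.500 | 0.500 | 0.500 | 0.500 |
| 0.2 | 0.799 | 0.739 | 0.649 | 0.500 |
| 0.3 | 0.895 | 0.816 | 0.698 | 0.500 |
| 0.5 | 0.982 | 0.885 | 0.741 | 0.500 |

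The sample size matters little. With 34 per arm (42 × 0.8 = 33.6, the maximum dropout in the SAP), P0 is 0.795 at d = 0.2 and 0.980 at d = 0.5. With 42 per arm it is 0.820 and 0.989.

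**The same formula applied to SPADI.** Here the SAP does give inputs: d = 10/15 = 0.667 and n = 35, and section 2 (Hypothesis) expects PAllow to do better. So P0 = Φ(0.667 × 4.183) = Φ(2.79) = 0.997. At q = 0.9, P = 0.9 × 0.997 + 0.1 × 0.003 = 0.898. At q = 0.75, P = 0.75 × 0.997 + 0.25 × 0.003 = 0.749. For equal q, SPADI at its planned effect identifies the arm slightly more often than pain acceptance does at the largest d in the table. The formula measures how guessable any directional result is. It does not single out a defect in section 5.

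**What withholding the row would achieve.** The row itself would then reveal nothing before sign-off (50%). SPADI and the remaining outcomes would still be in view. So would the per-protocol results: section 4 (Per-protocol population) makes membership depend on compliance with pain perception as recorded in the pain diary, and the note after Table 2 repeats the whole results table for that population. Overall masking is therefore not shown to improve.

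**The case for a change.** The strongest case is that equal q is unfair to this row. A superiority trial is run because the direction on SPADI is uncertain, whereas the direction on pain acceptance seems to follow from the instruction each arm received. With q = 0.9 for pain acceptance at d = 0.3, P is 0.816; with q = 0.75 for SPADI, it is 0.749. On those values the pain-acceptance row is the better clue. Nor does recording the item at baseline prevent this, because Table 2 reports change from baseline and a separation after allocation would still show.

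It stands that unmasking through this row is possible, and that a cautious team might prefer to release it later. It does not stand that the SAP is wrong as written. No value of q or d for this item can be drawn from the document, and without the item's definition neither the separation nor its direction can be judged. Delay also has a price: a listed secondary outcome would be analysed and interpreted after the authors had agreed their reading of the rest. To be effective, the delay would have to cover the per-protocol flag and results as well. The one open analytic choice, the working correlation, would be closed by naming it, not by staging the export.

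**Conclusion.** The concern does not hold. Section 5 describes a coherent procedure: separate export, coded arms, an external blinded statistician and sign-off before unblinding. The regression approach, adjustment covariates, weighting variables and alpha are stated in section 4 and the footnote to Table 2, so little is left for a correct guess to influence. No estimate, error rate, sample size or power figure changes.

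The possible loss of masking through this row ranges from none to near-certain identification (50% to 98% with 35 per arm), entirely according to assumed values of d and q. SPADI reaches 99.7% on the SAP's planning values if the reader is sure of the hypothesised direction. Whether to release one row later is a preference on which reasonable statisticians would differ, with a cost on each side. The conclusion rests on the SAP alone, which does not define the item; a definition showing strong separation by design would raise the chance of a correct guess but would still not make joint analysis an error.

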The per-protocol (PP) population is defined as participants who adhere to this protocol, defined by the following criteria in both groups:

- Are included in the AO population, and
- have attended at least 75 % of the scheduled on-site physiotherapist appointments, and
- have 75% compliance to pain perception during exercises (documented by pain diary), and
- have a minimum of 6 home-based training sessions weekly for the first 16 weeks of the 26 weeks intervention (documented by the exercise logbook), and
- do not engage in concomitant supervised exercise-based treatment for the shoulder and do not receive new, important interventions (e.g., no surgery, no shock-wave therapy or cortico-steroid injection) in the main trial phase

Primary analysis

The mean SPADI at each of the study time points, which includes the primary outcome SPADI at week 26, will be analyzed for each of the randomization groups in linear regression models; the models will be parameterized such that they directly produce inference on the difference between

STATISTICAL ANALYSIS PLAN PASE TRIAL

the randomization groups at each of the follow-up time points, beyond the difference that may be present at baseline. The analyses will account for repeated measurement by means of Generalized Estimating Equations (GEE).

Secondary outcome analysis

Secondary outcomes will be analysed similar to the primary outcome, in linear regression models with GEE.

Missing data

The presence of missing data at the various study time points is modelled by logistic regression models using age, sex, clinic, group allocation (masked) and baseline value as explanatory variables. Estimated probabilities for the data being not missing from these models will be used in inverse probability weights (IPW) to account for possible differential attrition; GEE adjusts inference to account for these weights (2, 9).

General statistical approach

Summary tables for quantitative variables included in publication are expected to include at least mean and standard deviation (SD) by treatment group. All summary tables for qualitative variables will display counts and percentages by treatment group. Baseline data are defined as the all measurements performed at the baseline visit.

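### Baseline SPADI is not a covariate in the primary outcome model, which costs precision; Section 4 also leaves the form of the footnote a adjustment open

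*SAP*

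**What the plan says.** **Effect.** SAP Section 4 (Intention-to-treat) makes the primary efficacy analysis a between-group difference in SPADI change at 26 weeks. Section 4 (Primary analysis) models mean SPADI at every visit by linear regression with GEE and reads off the group difference at follow-up "beyond the difference that may be present at baseline". Each group thus has its own free baseline mean. No outcome-model covariate is named there.

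**Adjustment.** The result columns of Tables 2 and 3 are labelled as adjusted, and footnote a reads "Adjusted for age, sex and clinic". These appear to be the randomisation factors: Section 3 stratifies by department and adds that "stratification by sex and age (± 35 years) are employed". How the three variables enter is not stated, nor whether age is continuous or split.

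**Missing data.** Section 4 models missingness with "age, sex, clinic, group allocation (masked) and baseline value as explanatory variables". The fitted probabilities "will be used in inverse probability weights (IPW) to account for possible differential attrition".

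**Sample size.** Section 3 bases it on a "mean difference of 10 points with a common standard deviation of 15". It says the calculation is "based on the change in the SPADI (primary outcome) from baseline to week 26", but not whether 15 is the SD of the change or of the score.

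**The concern.** In a randomised trial, measuring change from a free baseline difference is valid but is rarely the most precise choice. Using the baseline value as a covariate estimates the same effect with equal or smaller large-sample variance. Here the baseline value predicts who is missing but is left out of the outcome model, although it is usually a strong predictor of follow-up SPADI. The planned size has no reserve over 80% power, so the lost precision matters.

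Separately, two analysts following Section 4 and footnote a could fit different models: age, sex and clinic as main effects, or with visit-specific coefficients. The estimates differ, so the primary model is not fully fixed.

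**Working it through.** **1. The plan's own figure.** Inputs from Section 3 and the general approach in Section 4: difference 10, SD 15, two-sided 5%, power 80%. n per group = 2 × [15 × (1.960 + 0.842) / 10]² = 35.3, against 35 in the SAP. Power at 35 per group is 79.6% (normal) or 78.5% (t).

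**2. Change against baseline adjustment.** Let s0 and s1 be the baseline and week-26 SDs and r their correlation (assumed; not in the SAP). Per-patient variances are:
- change: s0² + s1² − 2·r·s0·s1
- baseline-adjusted: s1²(1 − r²)

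The first minus the second is (s0 − r·s1)², which is never negative. With s0 = s1 the ratio of the second to the first is (1 − r²) / [2(1 − r)] = (1 + r)/2.

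| r | variance ratio | SE ratio | SE smaller by |
|---|---|---|---|
| 0.3 | 0.65 | 0.806 | 19% |
| 0.5 | 0.75 | 0.866 | 13% |
| 0.7 | 0.85 | 0.922 | 8% |

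With unequal SDs, k = s1/s0, the ratio is k²(1 − r²) / (1 + k² − 2rk). Over r from 0.3 to 0.7 the SE cut is 29% to 21% at k = 0.8, and 11% to 1% at k = 1.25. For example, k = 1.25 and r = 0.7 give 0.797/0.8125 = 0.981, an SE cut of 1%.

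**3. Power at 35 per group** (normal approximation, equal SDs).

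| r | 15 is SD of change: change → baseline-adjusted | 15 is SD of score: change → baseline-adjusted |
|---|---|---|
| 0.3 | 79.6% → 93% | 65% → 83% |
| 0.5 | 79.6% → 90% | 80% → 90% |
| 0.7 | 79.6% → 86% | 95% → 97% |

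**4. With dropout and weighting.** Simulation of 84 patients and three visits, with about 20% dropout, weights as in the SAP, true difference 10, SD of change 15, assumed r = 0.5, independence working correlation and small-sample corrected SE. The assumed share of variance in change explained by the strata is 2 / 10 / 20%.

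| Outcome model | SE | Power (%) |
|---|---|---|
| no covariates | 3.78 / 3.79 / 3.78 | 75.1 / 75.2 / 75.8 |
| age, sex, clinic as main effects | 3.78 / 3.75 / 3.71 | 74.9 / 75.7 / 77.8 |
| age, sex, clinic by visit | 3.85 / 3.68 / 3.46 | 73.8 / 76.6 / 81.9 |
| baseline SPADI plus the three, by visit | 3.37 / 3.23 / 3.04 | 84.6 / 86.6 / 91.0 |

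Baseline SPADI alone gives 85.3 / 84.4 / 85.1% power, so it supplies most of the gain. The mean error of the estimate is at most 0.09 points in every model, so there is no bias to repair. A separate simulation with dropout and weighting gave SE cuts of about 9-19% over r from 0.3 to 0.7 (3.69 to 3.36 at r = 0.5).

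**5. The form of footnote a.** A main effect adds the same term to a patient's SPADI at every visit, so it subtracts out of the change. With complete data the estimates with and without main effects agreed to within 1.2e-13. With dropout, the baseline mean uses all patients and the follow-up means use those seen, so the terms no longer cancel. The SE then falls by 0-2% where the strata predict change only (3.78 to 3.78, up to 3.78 to 3.71), and by about 2-5% where they also predict SPADI level (for example 4.14 to 3.93 at r = 0.7). Main effects and visit-specific coefficients gave different significance verdicts in 3.2 / 3.8 / 5.7% of data sets.

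**The case against.** The planned contrast is valid under randomisation and matches a sample size based on change, so this is a matter of efficiency and not an error. The size of the gain rests on inputs absent from the SAP: the correlation, the SD ratio and what the SD of 15 refers to. All of that stands, which is why ranges are shown.

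Several stronger readings are tempting and fail:
- *Baseline SPADI is ignored.* It is not. It is the reference for the change and a predictor in the missing-data model; it is absent only as an outcome-model covariate.
- *The adjusted column is really unadjusted.* As main effects the three variables cancel exactly only with complete data. The SAP allows for up to 20% dropout, and then they can help a little.
- *Section 4 and footnote a contradict each other.* The table shells are part of the SAP and add covariates that Section 4 does not mention. That is missing detail, not two incompatible rules.
- *The adjustment acts only through the weights.* This is strained: the missingness model has five predictors, including group and baseline value, and footnote a lists three.

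The A/B coding and the signed consensus document limit steering towards an arm, but they do not specify a model.

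**Conclusion.** The point holds as a loss of precision in the primary analysis, without bias. Under equal SDs the SE would be about 19%, 13% or 8% smaller at assumed correlations of 0.3, 0.5 or 0.7. The gain is larger if SPADI varies less at follow-up than at baseline, and may be as little as 1% if it varies more. The roughly 75% power in the simulation should not be read as the cost of this choice alone; it also reflects about 68 of 84 patients followed up, the weighting and the corrected SE.

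The unstated form of footnote a is minor: main effects change the SE by roughly 0-5%, depending on how well the strata predict SPADI level. Baseline adjustment is a cheap improvement worth making, not a repair of an invalid analysis.

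**What to change.** In Section 4, name one primary model: a GEE of week-26 and week-52 SPADI on group, visit, group × visit, baseline SPADI × visit, department, sex and age, with the planned weights. State whether age is continuous or split at 35 years. Add the baseline value to the variables in footnote a of Tables 2 and 3. The column heading about change can stay, because with baseline SPADI in the model the group coefficient is the same whether the outcome is the follow-up score or the change.

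If the present change contrast is kept, one sentence should say whether age, sex and clinic enter as main effects or by visit.

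**Cost.** Wording only, before the blinded export; all variables are already collected. There are two small downsides:
- A few extra coefficients make a small-sample corrected robust SE (for example Mancl-DeRouen, with a t reference) advisable. In simulation the type I error of the proposed model was 6.3-7.8% uncorrected and 3.6-4.4% corrected. No uncorrected figure is at hand for the SAP's own model, so this is not a comparison.
- Patients with no follow-up visit contribute only through the weights. A three-visit model with a common baseline mean in both groups would keep their baseline rows with a similar gain, provided a correlated and not an independence working correlation is used.
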